APPENDIX 2. CONSIDERATIONS FOR REDUCING PAIN AND DISTRESS IN THE PEDIATRIC POPULATION

Although the study procedures and assessments required per protocol are classified as “No or Minimal Risk” (with the exception of DXA which may be classified as “Minor Increase over Minimal Risk”) according to the 2008 Guidance Document “Ethical Considerations for Clinical Trials on Medicinal Products Conducted with the Paediatric Population”, considerations for reducing pain in distress in participants <18 years of age are suggested below.

[figure not shown]
- The clinical trial may only be conducted if it patients the person concerned to as little burden and other foreseeable risks as possible.
- Physical and emotional pain should be prevented as much as possible, and effectively treated when unavoidable.
- In order to minimize pain, distress, and fear, facilities should be appropriate to childcare, and the personnel should be trained to look after children and supervised by experienced health care professionals. Staff should be trained to communicate with both parents (or legal representative) and children. Generally, this would assume non-adult patients are being studied at experienced pediatric centers.
- For most procedures, the child should always be accompanied by a trial-related staff member who could provide reassurance. At the sign of distress and/or dissent, the procedure should be stopped. A short pause to allow the child to feel in control, further explanation, and an assessment of the situation may be needed to reassure the child, or to decide to definitely abandon the procedure at the discretion of the Investigator.
- In all situations, investigations/interventions should be limited to the minimum required for obtaining valid data and performed using size-/age-appropriate material and devices, including limiting in advance the number of attempts for sampling.
- Study drug injections should only be performed by parents (or home health care professionals), unless the child is of suitable age and competency, and desires the ability to do so.
- Although almost all study procedures are classified as low risk (with the exception of DXA which may be classified as “minor increase over minimal risk”), risk should be continuously monitored and assessed by appropriate personnel.
- For assessments in which there is a psychological component, measures should be taken to minimize distress. For example, Tanner Staging assessments could utilize a diagram for the child to point to and indicate what stage they currently are, vs. having to have an exam without clothes.

[figure not shown]
A comment on benefit risk: Risk is very low, from procedures and/or known safety profile of the drug (both clinically and toxicologically, where large margins and preliminary data from juvenile toxicology studies have not identified any new or concerning safety concerns), and based on one representative example of rare genetic disorder of obesity impacting the MC4 pathway, there is the possibility of major benefit.

[figure not shown]
APPENDIX 3. FITZPATRICK SCALE

Skin Type	Skin Color	Characteristics
I	White; very fair; red or blond hair; blue eyes; freckles	Always burns, never tans
II	White; fair; red or blond hair; blue, hazel, or green eyes	Usually burns, tans with difficulty
III	Cream white; fair with any eye or hair color; very common	Sometimes mild burn, gradually tans
IV	Brown; typical Mediterranean Caucasian skin	Rarely burns, tans with ease
V	Dark Brown; mid-eastern skin types	Very rarely burns, tans very easily
VI	Black	Never burns, tans very easily

Fitzpatrick TB: Soleil et peau. J Med Esthet 1975;2:33034.

APPENDIX 5. INJECTION SITE EVALUATIONS

Injection sites will be assessed using a form similar to the depiction below at the time points outlined in the SoA, and in the setting of any injection site reaction adverse experience.

Local Skin Tolerability Assessment

Reaction	NONE	Mild	Moderate	Severe	Measurement (if applicable)
Erythema*					
Edema*					
Induration*					
Itching					
Pain or Tenderness*					
Other: _____					

* If present, region will be measured, length and width as appropriate.

Initials: _____

APPENDIX 6. ADVERSE EVENTS: DEFINITIONS AND PROCEDURES FOR RECORDING, EVALUATING, FOLLOW-UP, AND REPORTING

Definition of Adverse Event (AE)

AE Definition

• An AE is any untoward medical occurrence in a patient or clinical study patient, temporally associated with the use of study treatment, whether or not considered related to the study treatment.• NOTE: An AE can therefore be any unfavorable and unintended sign (including an abnormal laboratory finding), symptom, or disease (new or exacerbated) temporally associated with the use of study treatment.

Events Meeting the AE Definition

• Any abnormal laboratory test results (hematology, clinical chemistry, or urinalysis) or other safety assessments (eg, ECG, radiological scans, vital signs measurements), including those that worsen from baseline, considered clinically significant in the medical and scientific judgment of the investigator (ie, not related to progression of underlying disease).• Exacerbation of a chronic or intermittent pre-existing condition including either an increase in frequency and/or intensity of the condition.• New conditions detected or diagnosed after study treatment administration even though it may have been present before the start of the study.• Signs, symptoms, or the clinical sequelae of a suspected drug-drug interaction.• Signs, symptoms, or the clinical sequelae of a suspected overdose of either study treatment or a concomitant medication. Overdose per se will not be reported as an AE/SAE unless it is an intentional overdose taken with possible suicidal/self-harming intent. Such overdoses should be reported regardless of sequelae.• “Lack of efficacy” or “failure of expected pharmacological action” per se will not be reported as an AE or SAE. Such instances will be captured in the efficacy assessments. However, the signs, symptoms, and/or clinical sequelae resulting from lack of efficacy will be reported as AE or SAE if they fulfil the definition of an AE or SAE.

Events NOT Meeting the AE Definition

• Any clinically significant abnormal laboratory findings or other abnormal safety assessments which are associated with the underlying disease, unless judged by the investigator to be more severe than expected for the patient’s condition.• The disease/disorder being studied or expected progression, signs, or symptoms of the disease/disorder being studied, unless more severe than expected for the patient’s condition.• Medical or surgical procedure (eg, endoscopy, appendectomy): the condition that leads to the procedure is the AE.• Situations in which an untoward medical occurrence did not occur (social and/or convenience admission to a hospital).• Anticipated day-to-day fluctuations of pre-existing disease(s) or condition(s) present or detected at the start of the study that do not worsen.

Definition of Serious Adverse Event (SAE)

If an event is not an AE per definition above, then it cannot be an SAE even if serious conditions are met (eg, hospitalization for signs/symptoms of the disease under study, death due to progression of disease).

An SAE is defined as any untoward medical occurrence that, at any dose:
a. Results in death
b. Is life-threatening

The term 'life-threatening' in the definition of 'serious' refers to an event in which the patient was at risk of death at the time of the event. It does not refer to an event, which hypothetically might have caused death, if it were more severe.
c. Requires inpatient hospitalization or prolongation of existing hospitalization

In general, hospitalization signifies that the patient has been detained (usually involving at least an overnight stay) at the hospital or emergency ward for observation and/or treatment that would not have been appropriate in the physician's office or outpatient setting. Complications that occur during hospitalization are AEs. If a complication prolongs hospitalization or fulfills any other serious criteria, the event is serious. When in doubt as to whether "hospitalization" occurred or was necessary, the AE should be considered serious.Hospitalization for elective treatment of a pre-existing condition that did not worsen from baseline is not considered an AE.
d. Results in persistent disability/incapacity

The term disability means a substantial disruption of a person's ability to conduct normal life functions.This definition is not intended to include experiences of relatively minor medical significance such as uncomplicated headache, nausea, vomiting, diarrhea, influenza, and accidental trauma (eg, sprained ankle) which may interfere with or prevent everyday life functions but do not constitute a substantial disruption.
e. Is a congenital anomaly/birth defect
f. Important medical event

Medical or scientific judgment should be exercised in deciding whether SAE reporting is appropriate in other situations such as important medical events that may not be immediately life-threatening or result in death or hospitalization but may jeopardize the patient or may require medical or surgical intervention to prevent one of the other outcomes listed in the above definition. These events should usually be considered serious. 
Examples of such events include invasive or malignant cancers, intensive treatment in an emergency room or at home for allergic bronchospasm, blood dyscrasias, or convulsions that do not result in hospitalization, or development of drug dependency or drug abuse.

Recording and AE and/or SAE

AE and SAE Recording

- When an AE/SAE occurs, it is the responsibility of the investigator to review all documentation (eg, hospital progress notes, laboratory reports, and diagnostics reports) related to the event.
- The investigator will then record all relevant AE/SAE information in the eCRF.
- It is **not** acceptable for the investigator to send photocopies of the patient's medical records in lieu of completion of the AE/SAE CRF page.
- There may be instances when copies of medical records for certain cases are requested. In this case, all patient identifiers, with the exception of the patient number, will be redacted on the copies of the medical records before submission.
- The investigator will attempt to establish a diagnosis of the event based on signs, symptoms, and/or other clinical information. Whenever possible, the diagnosis (not the individual signs/symptoms) will be documented as the AE/SAE.

Assessment of Intensity

Intensity of all AEs including clinically significant treatment-emergent laboratory abnormalities, injection site reactions and potential systemic reactions will be graded according to the National Cancer Institute Common Terminology Criteria for Adverse Events (CTCAE), Version 5.0. The CTCAE grade refers to the severity of the AE and ranges from Grade 1 (mild AE), Grade 2 (moderate AE), Grade 3 (severe AE) and Grade 4 (life-threatening or disabling AE) to Grade 5 (death related to AE).

Adverse events not listed by the CTCAE will be graded as follows:

- Mild: An event that is easily tolerated by the patient, causing minimal discomfort and not interfering with everyday activities.
- Moderate: An event that causes sufficiently discomfort and interferes with normal everyday activities.
- Severe: An event that prevents normal everyday activities. An AE that is assessed as severe should not be confused with a SAE. Severe is a category utilized for rating the intensity of an event; and both AEs and SAEs can be assessed as severe.
- An event is defined as 'serious' when it meets at least 1 of the predefined outcomes as described in the definition of an SAE, NOT when it is rated as severe.

Assessment of Causality

- The investigator is obligated to assess the relationship between study treatment and each occurrence of each AE/SAE.
- A "reasonable possibility" of a relationship conveys that there are facts, evidence, and/or arguments to suggest a causal relationship, rather than a relationship cannot be ruled out.
- The investigator will use clinical judgment to determine the relationship.
- Alternative causes, such as underlying disease(s), concomitant therapy, and other risk factors, as well as the temporal relationship of the event to study treatment administration will be considered and investigated.
- The investigator will also consult the Investigator's Brochure (IB) and/or Product Information, for marketed products, in his/her assessment.

Assessment of Causality

- For each AE/SAE, the investigator **must** document in the medical notes that he/she has reviewed the AE/SAE and has provided an assessment of causality.
- There may be situations in which an SAE has occurred and the investigator has minimal information to include in the initial report. However, **it is very important that the investigator always make an assessment of causality for every event before the initial transmission of the SAE data.**
- The investigator may change his/her opinion of causality in light of follow-up information and send a SAE follow-up report with the updated causality assessment.
- The causality assessment is one of the criteria used when determining regulatory reporting requirements.

A medically qualified Investigator must assess the relationship of any AE (including SAEs) to the use of the study drug, as related or not related, based on clinical judgment and using all available information, and may include consideration of the following factors:

- Possible alternative causes of the AE, including the disease under treatment, pre-existing conditions, concomitant use of other drugs, and presence of environmental or genetic factors.
- The temporal association between study drug exposure and onset of the AE.
- Whether the manifestations of the AE are consistent with known actions or toxicity of the study drug.
- The AE resolved or improved with decreasing the dose or stopping use of the study drug (dechallenge). Judgment should be used if multiple products are discontinued at the same time.

The causal relationship between the study drug and the AE will be assessed using one of the following categories:

- **Not Related:** Factors consistent with an assessment of Not Related include:
 - Temporal relationship is lacking (eg, the event did not occur within a reasonable time frame following administration of the study drug); or
 - Other causative factors more likely explain the event (eg, a pre-existing condition, other concomitant treatments).
- **Related:** Factors consistent with an assessment of Related include:
 - There is a “reasonable possibility” of a relationship; i.e. there are facts, evidence, and/or arguments to suggest a causal relationship (not just that “a relationship cannot be ruled out”);
 - There is a positive temporal relationship (eg, the event occurred within a reasonable time frame following administration of study drug);
 - The AE is more likely explained by the investigational product than by another cause (ie, the AE shows a pattern consistent with previous knowledge of the investigational product or the class of the study drug).

Follow-up of AEs and SAEs

- The investigator is obligated to perform or arrange for the conduct of supplemental measurements and/or evaluations as medically indicated or as requested to elucidate the nature and/or causality of the AE or SAE as fully as possible. This may include additional laboratory tests or investigations, histopathological examinations, or consultation with other health care professionals.
- If a patient dies during participation in the study or during a recognized follow-up period, the investigator will provide a copy of any post-mortem findings including histopathology.
- New or updated information will be recorded in the originally completed CRF.
- The investigator will submit any updated SAE data to the Sponsor within 24 hours of receipt of the information.

Reporting of SAEs**SAE Reporting via an Electronic Data Collection Tool**

- The primary mechanism for reporting an SAE will be the electronic data collection tool.
- If the electronic system is unavailable for more than 24 hours, then the site will use the paper SAE data collection tool (see next section).
- The site will enter the SAE data into the electronic system as soon as it becomes available.
- After the study is completed at a given site, the electronic data collection tool will be taken off-line to prevent the entry of new data or changes to existing data.
- If a site receives a report of a new SAE from a study patient or receives updated data on a previously reported SAE after the electronic data collection tool has been taken off-line, then the site can report this information on a paper SAE form (see next section) or by telephone.

SAE Reporting to via Paper CRF

- Facsimile transmission of the SAE paper CRF is the preferred method to transmit this information
- In rare circumstances and in the absence of facsimile equipment, notification by telephone is acceptable with a copy of the SAE data collection tool sent by overnight mail or courier service.
- Initial notification via telephone does not replace the need for the investigator to complete and sign the SAE CRF pages within the designated reporting time frames.
- Contacts for SAE reporting will be provided to sites.

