#### **10.3.1 Overview of Adverse Events**

An overview summary table of AEs will be provided, including the number and percentage of patients reporting an AE for the following categories:

- Patients with at least one AE
- Patients with at least one treatment-emergent AE (TEAE)
- Patients with at least one TEAE related to study drug
- Patients with at least one TEAE leading to drug discontinuation
- Patients with at least one TEAE leading to study discontinuation
- Patients with at least one serious AE (SAE)
- Patients with at least one serious TEAE (SAE) related to study drug
- Patients with at least one serious TEAE
- Patients with AE resulting in death on study
- Patients who did not have an AE

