### **10.3.5 Death, Serious Adverse Events, Adverse Events Leading to Discontinuation**

Serious TEAEs, TEAEs leading to death, and TEAEs leading to study drug discontinuation will be summarized, in separate summary tables, by MedDRA SOC and PT, following the same methods specified in [Section 10.3.2](#). Furthermore, serious TEAEs will also be summarized, separately, by MedDRA SOC, PT, maximum severity/relationship/ relationship and maximum severity (defined in [Section 10.3.3](#) and [10.3.4](#)).

Additionally, separate patient listings also will be provided for the following: patient deaths, serious adverse events, and adverse events leading to study discontinuation and drug discontinuation.

The patient death listing will include any AEs that lead to an outcome of death, and will show the verbatim term, MedDRA SOC, MedDRA PT, event start date, date of death, severity, relationship to study drug, action taken with study drug, action taken, and outcome.

[figure not shown]
The SAE listing will include any AEs that are classified as an SAE, and will show the verbatim term, MedDRA SOC, MedDRA PT, event start date, event end date (or ongoing), SAE category, severity, relationship to study drug, action taken with study drug, action taken, and outcome.

The AEs leading to discontinuation listing will include any AEs that lead to an outcome of discontinuation or study drug withdrawn, and will show the verbatim term, MedDRA SOC, MedDRA PT, event start date, event end date (or ongoing), SAE indicator, severity, relationship to study drug, and outcome.

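### A death or admission that the investigator judges to be expected disease progression could be absent from every AE, SAE and death output, because Appendix 6 filters it out and the SAP counts deaths only through AEs

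*Protocol*

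**What the plan says.** **Protocol Appendix 6, events not meeting the AE definition.** The list includes "The disease/disorder being studied or expected progression, signs, or symptoms of the disease/disorder being studied, unless more severe than expected" for that patient's condition.

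**Protocol Appendix 6, SAE definition.** It opens with "If an event is not an AE per definition above, then it cannot be an SAE even if serious conditions are met", and gives as examples "hospitalization for signs/symptoms of the disease under study, death due to progression of disease".

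**Protocol Appendix 6, text pulling the other way.** Among events that are AEs it lists "Exacerbation of a chronic or intermittent pre-existing condition including either an increase in frequency and/or intensity of the condition", and also conditions newly found after treatment starts. Death and inpatient hospitalisation are themselves seriousness criteria. Under causality, the disease being treated is one of the alternative causes to be weighed for an event already recorded as an AE.

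**SAP 10.3.1.** The overview row for deaths is "Patients with AE resulting in death on study".

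**SAP 10.3.5.** For the tables: "Serious TEAEs, TEAEs leading to death, and TEAEs leading to study drug discontinuation will be summarized". For the listings: "The patient death listing will include any AEs that lead to an outcome of death" and "The SAE listing will include any AEs that are classified as an SAE". No death output is specified that does not depend on an AE record.

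**Protocol 9.19.1.** SAEs go to the sponsor within 24 hours. AEs are collected from consent, yet occurrences between consent and first treatment are sent to the medical history page and kept off the AE page.

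**The concern.** Safety and tolerability are a stated secondary objective (Protocol Section 4). The study has no control group (5.3) and is open-label (7.4), so a judgement that an event was due to the disease cannot be checked against a comparator. The usual safeguard is to record the event first and attribute it second. Appendix 6 allows the attribution to come first and to remove the event.

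The population makes that judgement hard to pin down. Patients have hypothalamic obesity after a non-malignant tumour and after surgery, chemotherapy or radiation (6.1). Appendix 6 does not say which of these is the disease whose progression is exempt. At stake are expedited reporting of a serious event, and safety tables that could show no deaths or SAEs when a patient has died or been admitted.

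**Working it through.** The plan gives no figure to reproduce here. The check is a trace through the text, followed by a calculation of scale.

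**Step 1: the filter.** For an event attributed to the disease, Appendix 6 works in sequence:

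- If it is more severe than expected for the patient, or is classed as an exacerbation or a new condition, it is an AE. If it is fatal or needs admission, it is then an SAE.
- If it is classed as expected progression, sign or symptom, and not more severe than expected, it is not an AE, and so not an SAE whatever the outcome.

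No benchmark for the expected severity is given. The death example in the SAE definition points towards the second branch; the exacerbation rule points towards the first. The branch taken is the investigator's decision.

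**Step 2: follow one on-treatment death down both branches.**

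| Output or action | Built from | Classed as AE | Classed as expected progression |
|---|---|---|---|
| Overview row for death (SAP 10.3.1) | AEs | counted | absent |
| Table of TEAEs leading to death (SAP 10.3.5) | TEAEs | counted | absent |
| Death listing (SAP 10.3.5) | AEs with fatal outcome | listed | absent |
| Serious TEAE tables and SAE listing (SAP 10.3.5) | AEs classed as SAEs | included | absent |
| 24-hour report (Protocol 9.19.1) | SAEs | triggered | not triggered |
| Disposition table and listing (SAP 6) | eCRF discontinuation reason | possible | possible |

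Disposition is marked as possible because the eCRF reason codes are not given in the documents.

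A filtered hospitalisation follows the same right-hand column, with one difference: a patient who is admitted and then stays on study does not appear among the discontinuations. Any procedure or drug given might be listed under SAP 8.3 or 8.4, but not as an admission.

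**Step 3: the SAP's safe defaults do not help.** Missing severity is set to severe (10.3.3) and missing relationship to related (10.3.4). Both act on AE records, so neither reaches an event that was never entered as an AE.

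**Step 4: scale only.** Planned enrolment is about 15 (Protocol 5.1).

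- One patient: 1/15 = 6.7%.
- Zero deaths, exact two-sided 95% upper limit: 1 − 0.025^(1/15) = 21.8%, so 0/15 reads as 0% (0 to 21.8%).
- One death, Clopper-Pearson: 1/15 reads as 6.7% (0.2 to 31.9%).

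The classification of one death decides which of the last two lines is reported. The intervals are for illustration; the SAP plans none for deaths.

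**The case against.** The strongest reply is that the bar is conditional. It applies only to an event that is not an AE, and disease events become AEs once they are more severe than expected. Many investigators would regard a death as exactly that. This stands. A reader might infer that Appendix 6 forbids any disease-attributed death or admission from being an SAE, so that such a death would certainly be missing. The documents do not support that; they support only that it could be missing, depending on classification.

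A reader might also infer that tumour regrowth or complications of severe obesity would be filtered out. The text does not establish this either. Exacerbations and newly found conditions are AEs, and invasive or malignant cancers are given as examples of important medical events. Moreover, the phrase about the disease under study qualifies the hospitalisation example only; the death example speaks simply of disease progression. What remains is that the term is undefined and the rules point in different directions.

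Third, the path is narrow. Patients are 6 to 40 years old with non-malignant tumours, are more than 6 months past tumour treatment, and receive 16 weeks of study drug. Current oncologic disease severe enough to interfere is excluded (6.2). This also stands: a death is unlikely, and a filtered admission is the more plausible case.

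Fourth, a death would not be unknown. Disposition may show it, Appendix 6 asks for post-mortem findings if a patient dies, and Protocol Section 9 requires immediate safety concerns to be discussed with the sponsor. That is correct, but none of these feeds a specified death output or replaces an SAE report.

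**Conclusion.** The concern holds in conditional form. A death or hospitalisation classed as expected progression, signs or symptoms of an undefined disease, and not as more severe than expected, is neither an AE nor an SAE under Appendix 6. It could then be missing from every AE, SAE and death output in the SAP. That outcome turns on one investigator's judgement, with no comparator against which to check it.

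The effect is one patient in about 15 (6.7%) per filtered event. The documents give no basis for a probability that it happens, and the 6.7% should not be read as one. The conclusion assumes that sites apply Appendix 6 as written and that no eCRF page outside the documents records all deaths independently of AEs. The primary efficacy analysis is not the issue here. The change should be made, because it removes a judgement-based filter from the safety results at almost no cost.

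**What to change.** 1. **SAP 10.3.1 and 10.3.5.** Build the death count and the death listing from all deaths on study regardless of AE status, with the attributed cause as a separate column.
2. **Protocol Appendix 6.** Reconcile the SAE sentence and its examples with the disease exclusion, the severity exception and the exacerbation rule. State that the exclusion does not apply to deaths or unplanned hospitalisations after first dose: these are recorded as AEs and reported as SAEs, and their relation to the disease is captured in the causality assessment. The existing exclusion for elective admissions stays. Deleting the SAE sentence alone is not enough, because the AE exclusion would remain and the SAP's SAE listing takes only AEs.
3. **Protocol 9.19.1.** Settle how serious events between consent and first dose are recorded, since that section both collects AEs from consent and sends pre-treatment occurrences to medical history.

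The cost is a wording change in Appendix 6 and 9.19.1, a small SAP edit, and possibly a few more SAE forms in a trial of about 15 patients.
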